#### **9.5.5. Visits 5 (Day 14±2)**

Visit procedures are identical to Visit 4 listed in section 9.5.4.

#### **9.5.6. Visit 6 (Day 21±1)**

Visit procedures are identical to Visit 5 listed in section 9.5.4.

Additionally, the Insulin Diary will be given to the subject to collect the following, daily:

- Total Daily Dose
- Total Daily Bolus

- Basal Rate

### 9.5.7. Visit 7 (Day 28±1)

The subject will fast after midnight the night before and arrive to the clinic at about 6-9 am the day of the planned hypoglycemia induction procedure. They will fast until the end of the hypoglycemia induction procedure the subsequent day. The subject will undergo the Hypoglycemia Induction Procedure as described in Section 9.4

1. AEs since the last visit will be recorded.
2. Concomitant medication review.
3. Assessment of vital signs, including measurement of BP, after a 5-minute seated rest
4. Physical examination, excluding breast, pelvic and genitourinary exams.
  - Measurement of height and weight
5. Performance of a 12-lead ECG (after subject has completed a 10-minute supine rest.)
6. Urine pregnancy test for women of childbearing potential.
7. Rapid urine drug screen.
8. The subject will have the following samples drawn:
  - CBC/CMP
  - Plasma glucagon (PK) before the Omnipod is removed
  - Immunogenicity sample
9. The subject's glucose, insulin, diary and pump data, if applicable, since the last visit will be reviewed. Subject data will be uploaded to the Medtronic Carelink Portal.
10. The Insulin Diary will be collected from the previous visit
11. The subject will complete the Gold Scale
12. The subject's Omnipod will be removed. Drug and Omnipod accountability will be completed.
13. The investigator will use the modified Draize scales (Appendix 5) to assess erythema and edema formation at the injection site at 10±5 minutes following removal of the Omnipod. Any injection site with a score > 0 for either erythema or edema at 10 minutes post-dosing will be re-evaluated for both at 60±5 minutes post-dosing. If any scores remain > 1 at the 60-minute evaluation, the subject may leave the clinic but will be instructed to contact study staff if the condition fails to resolve.
14. The subject will be reminded to refrain from using his or her own insulin until the hypoglycemia induction procedure is complete.
15. IV lines are inserted in both upper extremities for IV insulin and glucose infusion, and for venous sampling.
16. Plasma glucose is measured using a laboratory quality instrument, e.g. the YSI 2300 or 2900 that will be used for the clamping procedure.

17. Plasma Glucose will be maintained in the 80-120 mg/dL range until as described in section 9.4.
18. The subject will undergo the hypoglycemia induction procedure and normalization to euglycemia, per Section 9.4.
19. At the end of the treatment visit, the subject will discontinue use of the iPRO2mylog.
20. For the rest of the study, the subject will continue their standard of care for diabetes management. Study drug and devices are no longer used.

**9.5.9. Visit 8 (Week 12±1 week)**

**CGM Resumption for 3-Month Follow Up**

This visit can occur at any time of day as is least cumbersome for subject and clinic scheduling. The following will occur.

1. Concomitant Medication Review
2. AEs since the last visit will be recorded.
3. The subject's dedicated blood glucose meter and iPRO2 recorder will be retrieved from storage and the subject will resume use as well as the iPRO2mylog diary with the insertion of a new CGM sensor.
4. The subject will be given a supply of BGM strips until the next visit a week later, to verify calibration of the CGM.
5. The Insulin Diary will be given to the subject to collect the following, daily:
  - Total Daily Dose
  - Total Daily Bolus
  - Basal Rate
6. The next visit will be scheduled.

**9.5.10. Visit 9 (Week 13±1 Week) 3-Month Follow Up**

The subject will arrive to the clinic at about 6-9 am the day of the planned hypoglycemia induction procedure. The subjects will undergo this inpatient CRU visit.

1. AEs since the last visit will be recorded.
2. Concomitant medication review.
3. Assessment of vital signs, including measurement of BP, after a 5-minute seated rest
4. Urine pregnancy test for women of childbearing potential.
5. The subject will be reminded to refrain from using his or her own insulin until the hypoglycemia induction procedure is complete.
6. The subject will complete the Gold Scale

7. Subject data including CGM, insulin utilization, electronic diary data will be uploaded to the MedTronic iPRO2 platform.
8. The Insulin Diary will be collected from the previous visit.
9. IV lines are inserted in both upper extremities for IV insulin and glucose infusion, and for venous sampling.
10. Plasma glucose is measured using a laboratory quality instrument, e.g. the YSI 2300 or 2900 that will be used for the clamping procedure.
11. Plasma Glucose will be maintained in the 80-120 mg/dL range as described in section 9.4.
12. The subject will undergo the hypoglycemia induction procedure and normalization to euglycemia, per Section 9.4
13. The subject will have the following sample drawn:
  - Immunogenicity Sample

#### **9.5.11. Visit 10 (Week 25±1 Week)**

##### **CGM Resumption for 6-Month Follow Up**

The visit procedures are identical to those on Visit 8 week 12 as described in section 9.5.8.

#### **9.5.12. Visit 11 (Week 26±1 Week)**

##### **6-Month Follow Up and Completion of Study**

The visit procedures are identical to those on Visit 9 as described in section 9.5.9 with the additions that the following is performed:

1. A physical examination, excluding breast, pelvic and genitourinary exams.
2. The subject will have the following samples drawn:
  - CBC/CMP
3. Final discharge of the subject from the study.

### **9.6. Subject Withdrawal**

Subjects may withdraw from the study at any time at their own request, or they may be withdrawn at any time at the discretion of the investigator or Sponsor for safety, behavioral or administrative reasons. If a subject does not return for a scheduled visit, every effort should be made to contact the subject to determine the reason(s) why the subject failed to return for the scheduled visit, and to reschedule the missed visit. In all circumstances, every effort should be made to document subject outcome. Information regarding the reason for not completing the study will be recorded in the CRF. The investigator should inquire about the reason for withdrawal, request that the subject return for a final visit, and follow-up with the subject

regarding any unresolved AEs. It will be documented whether each subject completed the study. Any subject who receives at least one treatment dose of study medication will be included in the safety analysis.

If a decision by the investigator or sponsor is made to withdraw a subject, a final visit should be scheduled soon after the decision to withdraw is made. The subject will be asked to return to site for the assessments listed in Section 9.5.11.

If the subject withdraws from the study and also withdraws consent, no further evaluations should be performed, and no additional data should be collected. The Sponsor may retain and continue to use any data collected before such withdrawal of consent

Approved

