## **7.2. Interruption and Termination of Dosing**

Dosing will be paused for any SAE that occurs in a subject receiving treatment until causality is fully assessed by the Investigator. Dosing will cease if the SAE is determined to be either drug-related or unknown, and may resume if the SAE is determined to be not drug-related by the investigator and the Sponsor agrees.

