### 10.11. Withdrawal Due to Adverse Events

Withdrawal due to AE should be distinguished from withdrawal due to insufficient response, and recorded on the appropriate CRF. When a subject withdraws due to an SAE, the SAE must be reported in accordance with the reporting requirements (see [Section 10.13](#)).

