### 11.1. Efficacy

The primary aim of the study is to evaluate change from baseline of plasma epinephrine concentration during induced hypoglycemia with PG <50 mg/dl between placebo and CSGI after 4 weeks of blinded treatment. The null hypothesis to be tested is there is no difference in the change from baseline to 4 weeks between the two groups for plasma epinephrine concentration during induced hypoglycemia with PG <50 mg/dl. Two-group t-test will be implemented for each hypothesis test.

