### **11.1.3. Sample Size Calculation:**

The primary hypothesis is to evaluate change from baseline to 4 weeks of plasma epinephrine concentration after 30 minutes of induced hypoglycemia with plasma glucose <50mg/dL between treatment groups. Sample size is based on a closed hierarchical hypothesis test as described above in section 13.1.1.

Using this method, an alpha of 5% will be preserved for each hypothesis test where the next ordered test will only be conducted if statistical significance is achieved for that hypothesis. Final calculations are based on 80% power and an alpha of 5%, to demonstrate a plasma epinephrine increase compared to placebo of 1.5 nmol/l given and SD of 1.34 nmol/l at an induced PG of 50 mg/dl. Sixteen subjects per treatment group (CSGI high dose, CSGI low dose, and placebo) are required based on the minimum sample size estimate for a comparison.

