### **7.1.1 Intent-to-treat Population (ITT or All Randomized)**

The ITT population includes all randomized subjects. The ITT population will be analyzed according to the treatment group to which subjects were randomized.

ITT population will be used for primary and secondary efficacy endpoints.

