## 7.4 Subject Disposition

Subject disposition will be summarized as follows:

- The number of subjects who were screened, screen failures, randomized and who are in each analysis population will be summarized by treatment group and overall.
- The number of early withdrawals and the reasons for withdrawals will be tabulated by treatment group and overall for ITT population

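### The protocol makes no provision for a subject who stops study drug but still consents to attend the Week 4 induction, and the ITT primary test has no rule for the value then missing

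*Protocol*

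**What the plan says.** **Endpoint.** SAP 4.1 and 7.10.1 define the primary endpoint as percent change in epinephrine from Induction 1 to Induction 2, the latter at Visit 7. Without that induction there is no primary value.

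**Stopping drug.** Protocol 7.2 provides for dosing to end while a subject is in the study: "Dosing will cease if the SAE is determined to be either drug-related or unknown". It does not say whether that subject then attends Visit 7.

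**Leaving the study.** Protocol 9.6 deals with withdrawal from the study. For withdrawals decided by the investigator or sponsor, "a final visit should be scheduled soon after the decision to withdraw is made", with the assessments of Section 9.5.11. A subject who withdraws at their own request is asked to return for a final visit. Protocol 10.11 is also framed in terms of withdrawal: "Withdrawal due to AE should be distinguished from withdrawal due to insufficient response". So is SAP 7.4: "The number of early withdrawals and the reasons for withdrawals will be tabulated by treatment group and overall for ITT population". SAP 7.11.1 tabulates adverse events leading to withdrawal. None of these has a separate category for stopping drug while staying in the study.

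**Analysis.** Under SAP 7.1.1 the ITT set is everyone randomized and is used for the primary endpoint: "The ITT population will be analyzed according to the treatment group to which subjects were randomized". SAP 7.10.2 specifies a two-group t-test and gives no rule for a missing Visit 7 value in that set. SAP 7.10.3 places all three missing-outcome sensitivity analyses in the per-protocol set, which SAP 7.1.2 limits to subjects who participate through day 27 without major deviations.

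**The concern.** A subject who stops the pump at, say, Day 10 and still consents can in principle have epinephrine measured at Visit 7. The plan neither asks for this nor rules it out, so sites may differ. Wherever stopping is handled as withdrawal, the primary outcome is not collected, although it could have been.

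At stake is what the ITT result means. The set is labelled all randomized, but a t-test without a missing-data rule uses only subjects with a Visit 7 value. If those who stop would have had different Week 4 changes from those who continue, and if stopping is not balanced, the comparison is between selected groups. The sensitivity analyses that should show how much this matters are run in a set from which early leavers have already been removed.

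**Working it through.** **1. Reproduce the plan's sample size.** Inputs from Protocol 11.1.3: 80% power, 5% alpha and a "plasma epinephrine increase compared to placebo of 1.5 nmol/l given and SD of 1.34 nmol/l". Protocol 11.1 gives a two-group t-test and a no-difference null ("The null hypothesis to be tested is there is no difference in the change from baseline to 4 weeks between the two groups"), and SAP 7.10.1 has a not-equal alternative, so the test is two-sided. The noncentral t gives power 0.782 at 13 per group and 0.813 at 14. Three groups of 14 give 42, matching the N=42 in the Synopsis. Randomizing 48 implies an attrition allowance of 1 − 42/48 = 12.5%. At the full 16 per group, power for one dose v placebo is 0.865.

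**2. Does the withdrawal visit supply a Week 4 value?** Section 9.6 points to 9.5.11. In the body of the protocol, 9.5.11 is Visit 10, which repeats Visit 8: CGM insertion, no induction. In the table of contents, 9.5.11 is Visit 11, which includes an induction through the Visit 9 procedures. The first reading gives no epinephrine value. The second gives one at whatever time the subject happened to withdraw, not at Visit 7. The two passages conflict and must be reconciled, but neither yields the primary endpoint.

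**3. Do the sensitivity analyses recover these subjects?** SAP 7.10.3 imputes for subjects lost to follow-up or missing the outcome, but within the per-protocol set. A subject who left before day 27 is not in that set. The imputation can reach only someone who took part through day 27 and still lacks the value.

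**4. Size of the selection, as an illustration.** Assumptions: k of 16 high-dose subjects stop and would show no gain at Week 4, all other CSGI subjects gain 1.5 nmol/l over placebo, and placebo is complete. The complete-case estimate stays at 1.5.

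- High dose v placebo: all-randomized effect = 1.5 × (16 − k)/16.
- Combined CSGI v placebo (first in the hierarchy, 32 v 16): all-randomized effect = 1.5 × (32 − k)/32.

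| k | High dose: effect | Complete-case excess | Combined: effect | Complete-case excess |
|---|---|---|---|---|
| 2 | 1.31 | 14% | 1.41 | 7% |
| 3 | 1.22 | 23% | 1.36 | 10% |
| 4 | 1.13 | 33% | 1.31 | 14% |

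**5. Effect of retention on power, under the same assumptions.** High dose v placebo, SD held at 1.34:

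- k = 2: stoppers excluded (14 v 16, effect 1.5), 84.0%; retained (16 v 16, effect 1.31), 76.4%.
- k = 4: stoppers excluded (12 v 16, effect 1.5), 80.6%; retained (16 v 16, effect 1.13), 63.2%.

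Retention lowers power here, because it restores subjects assumed to have no gain.

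**6. What selection does when there is no effect.** Assume placebo is complete and CSGI stoppers would have had a change 0.5 to 1 SD below those who continue. The spurious difference is (fraction lost) × (0.5 to 1) × 1.34. With 12.5% of CSGI lost it is 0.08 to 0.17 nmol/l, and the combined test rejects 5.4% to 6.8% of the time. With 25% lost it is 0.17 to 0.34 nmol/l, with rejection 6.7% to 11.8%, against a nominal 5%.

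All these figures are on the absolute-change scale of the sample-size calculation. The SAP primary endpoint is percent change, for which no effect or SD is given.

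**The case against.** **Section 9.6 does not equate stopping the pump with leaving the study.** A reader might infer that it does. The text does not support this: 9.6 addresses study withdrawal, and 7.2 handles ceased dosing separately without withdrawing anyone. Protocol 9.5 times visits from randomization, so a subject who stops drug and is not withdrawn still has Visit 7 on the schedule and, on attending, stays in the ITT comparison. Only the pregnancy rule in 10.16 expressly joins the end of treatment to leaving. This stands: the defect is silence, not a rule that removes such subjects.

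**Section 9.6 contains mitigating text.** It asks for every effort to reschedule missed visits and to document outcome, and bars further evaluation only when consent is also withdrawn. The prompt final visit is written for investigator or sponsor withdrawals. This also stands, but none of it names the Week 4 induction.

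**Stopping may not differ by arm.** A reader might infer that more subjects will stop on CSGI. The documents give no stopping rate by arm. Placebo is the same vehicle (8.6.1.2), infused at matched rates (7.1, 8.4). The glucose rise expected in 6.1.2.4 and the drug-related SAE rule in 7.2 give only an indirect reason. The imbalance is therefore an assumption.

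**The larger percentages are not those of the first test.** The 14% to 33% belongs to high dose v placebo. For combined CSGI the same stoppers give 7% to 14%.

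**Conclusion.** The gap is real and worth closing. Following the text as written can lose primary outcomes that could have been obtained, from a set the SAP defines as everyone randomized, and the planned sensitivity analyses do not reach those subjects. This rests on reading the passages together and needs no assumption about which arm stops more.

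The size is not known. The 14% to 33% (high dose) and 7% to 14% (combined) depend on zero gain in stoppers, complete placebo data and the absolute-change scale. Balanced loss would still cost power: with two lost in each arm, one dose v placebo falls from 86.5% to 81.3%. It should not be inferred from this that retaining stoppers restores power; under the zero-gain assumption it reduces it. The case for retention is that the estimate then describes the randomized groups.

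**What to change.** **Protocol.** In 9.6, cross-referenced from 7.2, separate stopping study drug from withdrawing from the study. State that subjects who have stopped drug and still consent keep the scheduled Visit 7 assessment, subject to the investigator's judgement that it is suitable and to the existing bar in 10.16. Leave the rules for when dosing stops unchanged. Reconcile the 9.5.11 reference with the visit intended.

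**SAP.** State that such a Visit 7 value enters the ITT primary analysis in the randomized arm. Run the missing-outcome sensitivity analyses of 7.10.3 in the ITT set. Tabulate drug discontinuation and study withdrawal separately in 7.4 and 7.11.1.

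**Cost.** A short amendment and a few SAP changes; the visit is already on the schedule. The new tabulation needs a recorded stop date and reason. SAP 7.2.6 already uses the date of last dosing, but SAP Section 10 says treatment compliance was not captured, so the source must be confirmed. The statistical cost is dilution: off-drug Week 4 values can pull the ITT estimate down and lower power, for example from 84.0% to 76.4% for high dose v placebo with two zero-gain stoppers. The per-protocol analysis gives the on-drug contrast only if early stopping counts as a major deviation, which SAP 7.5 leaves to blinded review and should settle in advance.

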**Table 6: Schedule of Assessments**

Assessment	V1	V2	V3	V4	V5	V6	V7	V8	V9	V10	V11
	Screening Day 25+ 5	CGM Placement Day -7	Baseline Day 1	Safety Check Day 7±1	CGM Placement Day 14±1	CGM Placement Day 21±1	Treatment End Day 27-28±1	CGM Placement 12±1 weeks	3-Month F-up +13±1 weeks	CGM Placement 25±1 weeks	6-Month F-up 26±1 weeks
Informed consent	X										
Demographic data	X										
Concomitant medications	X		X	X	X	X	X	X	X	X	X
Eligibility review	X	X	X								
Vital signs	X		X				X		X		X
Physical exam a	X						X				X
ECG	X						X				
Urine pregnancy test	X		X				X		X		X
Rapid urine drug screen	X						X				
CBC/CMP	X		X				X				X
HbA1c	X										
Subject glucose testing data review and insulin dose adjustment		X	X	X	X	X	X				
Randomization			X								

Assessment	V1	V2	V3	V4	V5	V6	V7	V8	V9	V10	V11
	Screening Day -- 25±5	CGM Placement Day -7	Baseline Day 1	Safety Check Day 7±1	CGM Placement Day 14±1	CGM Placement Day 21±1	Treatment End Day 27-28±1	CGM Placement 12±1 weeks	3-Month F-up 13±1 weeks	CGM Placement 25±1 weeks	6-Month F-up 26±1 weeks
Hypoglycemia induction			X				X		X		X
Plasma glucose (YSI) b			X				X		X		X
Hormone levels c			X d				X d		X		X
Gold scale & Hypoglycemia symptom questionnaire	X e		X				X		X		X
Blood samples for immunogenicity testing	X				X		X		X		X
Insert new CGM		X	X	X	X	X		X		X	
Retrieve prior CGM			X	X	X	X	X		X		X
Account for and Dispense vials & OmniPods			X	X	X	X	X f				
Subject questionnaire for InjectionSite Discomfort			X	X							

Assessment	V1	V2	V3	V4	V5	V6	V7	V8	V9	V10	V11
	Screening Day -- 25±5	CGM Placement Day -7	Baseline Day 1	Safety Check Day 7±1	CGM Placement Day 14±1	CGM Placement Day 21±1	Treatment End Day 27-28±1	CGM Placement 12±1 weeks	3-Month F-up 13±1 weeks	CGM Placement V6 +25±1 weeks	6-Month F-up 26±1 weeks
Draize scales				X			X				
Subject Insulin Diary g		X	X h			X	X h	X	X h	X	X h
Review AE		X	X	X	X	X	X	X	X	X	X

a Excluding breast and pelvic/genitourinary exam.

b Every 5 minutes during hypoglycemia induction

c Norepinephrine, glucagon, cortisol and growth hormone 10 minutes apart when PG is at 100 mg/dl and 50 mg/dl, 4 times total per hypoglycemia procedure.

d For glucagon prior to hypoglycemia induction at baseline day -1 and before the removing of the Omnipod at day 27.

e Only the Gold Scale is administered at screening

f Accounting only, no dispensing.

g Subject Insulin Diary will be provided to the subject to collect the following: Total Daily Dose, Total Daily Bolus, Total Basal.

h Subject Insulin Diary is only collected from the subject

## 10. ASSESSMENTS

Every effort should be made to ensure that the required tests and procedures are completed as described. However, it is anticipated that there may be circumstances outside the control of the investigator, who will take all steps necessary to ensure the safety and well-being of the subject. When a protocol-required test cannot be performed, the investigator will document the reason(s) and any corrective and preventive actions taken to ensure that study processes are adhered to as soon as possible. The study team and the sponsor will be informed of these incidents in a timely fashion.

For all blood and urine collections, an effort should be made to obtain these samples at roughly the same time of day (i.e., morning or afternoon) across all visits as well as at the time periods specified in the Schedule of Activities. In addition, visits to the site must occur within the pre-defined windows outlined in this protocol, otherwise they will be considered as protocol deviations.

### 10.1. Estimated Blood Volume Drawn through Time

At each hypoglycemia induction there will be approximately 50 blood samples for PG determination of about 2cc each. Additional sample requirements are shown in (Table 7). The largest blood volume drawn over any 3-month period is < 350 ml (less than 24 tablespoons).

**Table 7: Frequency and Volume of Blood Collections**

Assay	Sample Volume (mL)	Screening	V3	V7	V9	V11	Total (mL)
Plasma Glucose (YSI)*	2		50	50	50	50	400
Serum Ethanol	5	1					5
Chemistry (14 gen chem. incl. ALT, AST, bilirubin, albumin)	7.5	1	1	1		1	30
C-peptide, serum	2.5	1					2.5
Hematology (Hemoglobin, Hematocrit, Platelet Count, MPV, RDW, RBC Count, WBC Count, MCV, MCH, MCHC, - no differential)	3.5	1	1	1		1	14
HbA1c (included in hematology)		1					0

Assay	Sample Volume (mL)	Screening	V3	V7	V9	V11	Total (mL)
Hormone levels: Cortisol, Norepinephrine, Growth hormone	2		4	4	4	4	32
Hormone levels: Plasma epinephrine	4		4	4	4	4	64
Glucagon	8.5		4	5	4	4	144.5
Immunogenicity (Anti-glucagon antibody)	3.5	1		1	1	1	14
Total/Visit (mL)		22	169	181	161.5	172.5	706

a Single PG measurements at bedside via rapid glucose analyzer.

